- What features and functionalities could better help you support patients throughout their treatment? What information do you see as critical to provide to TB patients throughout their treatment? What functions would facilitate you managing a large patient cohort effectively? What name would you recommend for the app?

Method and analysis: All focus group sessions and interviews will be audio-recorded and transcribed verbatim for analysis. Identified glitches, feedback, recommendations will be synthesized for programmers. Steps will be repeated after refinements made.

Aim 3. Assess feasibility, usability, perceived usefulness, and initial efficacy of the resulting product in a pilot RCT. By conducting a pilot RCT, mimicking all of the major essentials of definitive trial, I will determine the feasibility, usability, perceived usefulness, and further refine intervention in congruence with iterative framework and estimate effect size for a future definitive evaluation. The goal is to increase TB treatment success rates to WHO minimum 85% target and reduce rates of poor outcomes (e.g., default, drug resistance).

Sample size: To detect a 15% increase in treatment success with 80% power and an α of 0.05 (two-tailed) a sample size total of 348 is required. Based on recommended sample size calculations for pilot RCT,⁵⁶ 9% of sample size of main planned trial is needed, 35 participants. The power calculation is only applicable to the primary outcome of treatment success and not for the subgroup analyses. To be cautious and account for an estimated 20% attrition, the recruitment target was increased to 46.

Setting: Health Region V described above.

Recruitment: All patients newly diagnosed with TB meeting inclusion criteria will be notified of the study by clinic staff and referred to research staff to receive full explanation and have questions answered. Signed informed consent will be obtained for all participants. A recruitment log will be maintained to document screened patients and reasons for declining participation. Patients will be enrolled on an ongoing basis, and recruitment is estimated to be completed in 4 months after start of recruitment.

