Inclusion/Exclusion criteria: Patients 18 years of age or older starting TB treatment for the first time, with no known TB drug resistance, HIV negative, owning or having regular access to a smartphone, and who are able to operate the mobile phone to communicate or have someone able to assist. Excluded will be patients who are severely ill (i.e., requiring hospitalization) or reside in the same household with another study participant. Patients with known drug resistance and those with HIV co-infection will be excluded because their care is managed separately and the treatment regimens and duration differ. Screened patients who do not meet study eligibility will have specific screening data (including gender, age and reason for exclusion) entered into the study database which data will be helpful in examining the patient population and feasibility of enrollment criteria.

Randomization: Participants will be randomized to usual care and usual care plus app-based intervention at a ratio of 1:1 in blocks of 10 to ensure balanced representation in both arms. Random allocation sequence will be generated using <http://www.randomization.com/>. Opaque envelopes sequentially numbered and sealed will be used for treatment allocation concealment. Due to the nature of the intervention, blinding to the group allocation cannot be achieved for research staff. Clinicians will not be made aware of the group allocation unless their patient informs them.

Usual care: Drug treatment and patient monitoring are provided free of charge in the public health system. Usual care consists of outpatient treatment management from the time of diagnosis (unless symptoms are severe and hospitalization is recommended), routine clinical and laboratory tests, and follow-up appointments determined by the clinician. In general, patients receive 1-2 month's supply of medication and are asked to return monthly for follow-up appointments, or earlier if experiencing any problems. Patients with first treatment receive a 6-month regimen consisting of a two-month *intensive* phase of four drugs (rifampicin, isoniazid, pyrazinamide, and ethambutol or streptomycin), followed by a four-month *continuation* phase with isoniazid and rifampin daily or 3 times a week.⁵⁷ Three of the four medications are provided in a combined pill, therefore testing isoniazid urine metabolite is an indicator of all medications ingestion except for ethambutol.

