Program evaluation		Feasibility, ease of use, home drug metabolite testing, recommendations	Descriptive/qualitative	X
Secondary outcomes				
Global Health PROMIS SFv1.1	I>C	CDE outcome for self-management		X X
WHOQoL-BREF measures				
Level of engagement*		# of messages: notification, side effects, questions	Descriptive	X X X X
TB knowledge	I > C	Change in TB knowledge score	t-test	X
Appointment attendance	I > C	Mean proportion	χ^2 test	X X X
Cost accounting		Log of intervention costs	Descriptive	X X X X
Subgroup analyses				
Gender	Female>male			
Age	Older>younger			
Mobile phone access type	Personal>shared			
Time to clinic	$\leq 30 > 30$ min		χ^2 test	

Note: I=intervention, C=control; PROMIS= Patient-Reported Outcomes Measurement Information System; CDE=common data elements; T0 Screening, T1 Baseline, T2, 2 months, T3 6 months, * = data collected from intervention group only

Secondary outcomes include the Global Health Patient-Reported Outcomes Measurement Information System (PROMIS) short form,⁶² TB knowledge, level of tool engagement, appointment attendance and cost accounting. The Global Health SF is a recommended outcome measure for self-management, includes 10 items, is available in the Spanish language, and can be integrated into REDCap. TB knowledge will be assessed using items from the Tuberculosis Knowledge Assessment Questionnaire at pre and post-intervention.²⁵ Items include questions focused on exploring knowledge about: causes and symptoms of TB (5 items), TB transmission (4 items), TB treatment (2 items), and TB prevention (5 items)(Appendix C). The questions are structured to answer (yes, no, I don't know). For those randomized to app, I will evaluate the level of engagement with the intervention (e.g., percentage of notification without a reminder, number of questions, number of reported side effects).

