Data Analysis/Interpretation: All analyses will be based on intention-to-treat. Statistical analyses will be performed using IBM SPSS, version 20 (Chicago, IL). Independent-sample *t*-tests will be conducted for continuous outcomes and chi-square test for dichotomous or categorical variables. Standard descriptive statistics of frequency, central tendency, and dispersion will be used to describe each sample. A p-value less than 0.05 will be set to detect a statistically significant difference for all analyses. I will compare group baseline characteristics including: age, gender, education, travel time to center, take other medication on a regular basis, and baseline TB knowledge. For qualitative data, the transcripts will be entered into Nvivo to organize and iteratively code using thematic and descriptive qualitative methods.^{64,65}

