Sample size: To detect a 15% increase in treatment success with 80% power and an α of 0.05 (two-tailed) a sample size total of 348 is required. Based on recommended sample size calculations for pilot RCT,⁵⁵ 9% of sample size of main planned trial is needed, 35 participants. The power calculation is only applicable to the primary outcome of treatment success and not for the subgroup analyses. To be cautious and account for an estimated 20% attrition, the recruitment target was increased to 46.

Data Analysis/Interpretation: All analyses will be based on intention-to-treat. Statistical analyses will be performed using IBM SPSS, version 20 (Chicago, IL). Independent-sample *t*-tests will be conducted for continuous outcomes and chi-square test for dichotomous or categorical variables. Standard descriptive statistics of frequency, central tendency, and dispersion will be used to describe each sample. A p-value less than 0.05 will be set to detect a statistically significant difference for all analyses. I will compare group baseline characteristics including: age, gender, education, travel time to center, take other medication on a regular basis, and baseline TB knowledge. For qualitative data, the transcripts will be entered into Nvivo to organize and iteratively code using thematic and descriptive qualitative methods.

REFERENCES

1. World Health Organization. Global Tuberculosis Report 2015. Geneva, Switzerland: WHO, 2015.
2. World Health Organization. End TB Strategy. 2015.
3. Mitchison DA. How drug resistance emerges as a result of poor compliance during short course chemotherapy for tuberculosis. *Int J Tuberc Lung Dis* 1998; **2**(1): 10-5.
6. World Health Organization. What is DOTS? A guide to understanding the WHO-recommended TB control strategy known as DOTS, 1999.
8. United Nations. Sustainable Development Goals. 2015. <http://www.un.org/sustainabledevelopment/sustainable-development-goals/>.

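### TB knowledge is tested by a t-test on the change score; ANCOVA on the same two scores would usually be more precise (minor, secondary outcome)

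*Combined protocol and SAP*

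**What the plan says.** The outcomes table (Table 5, overview of variables and hypotheses; an earlier table carries the same number) lists TB knowledge as a secondary outcome. The hypothesis is that the intervention arm does better, the measure is "Change in TB knowledge score", and the analysis is a t-test. The Outcomes text adds: "TB knowledge will be assessed using items from the Tuberculosis Knowledge Assessment Questionnaire at pre and post-intervention". The questionnaire has 5 + 4 + 2 + 5 = 16 items.

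The Data Analysis/Interpretation paragraph, which is repeated under Statistical Design and Power, gives the general rule: independent-sample t-tests "will be conducted for continuous outcomes and chi-square test for dichotomous or categorical variables". No ANCOVA, regression or other baseline-adjusted model appears in either place. Baseline knowledge does appear, but only in the list of characteristics to be compared between the arms, which ends "take other medication on a regular basis, and baseline TB knowledge".

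Participants are randomised "at a ratio of 1:1 in blocks of 10 to ensure balanced representation in both arms"; no stratification is described. The Sample size paragraph says that "9% of sample size of main planned trial is needed, 35 participants" and sets a recruitment target of 46. It limits the power calculation to treatment success.

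**The concern.** Subtracting the baseline score adjusts for baseline with a regression slope fixed at 1. ANCOVA estimates that slope. Unless the true slope is close to 1, the change score carries avoidable noise and over-corrects for any chance difference between the arms at the start. An arm that happens to start lower will tend to show the larger gain through regression to the mean.

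A slope of exactly 1 is unlikely here. If each item scores one point (an assumption; the scoring is not stated), the scale stops at 16 and patients who start high have less room to gain. Blocked allocation balances numbers per arm and balances baseline knowledge only in expectation, and chance differences are largest in a small pilot.

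At stake is a wider interval than necessary, and an estimate more exposed to chance, for one secondary between-arm comparison.

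**Working it through.** The plan gives no power, SD or correlation for TB knowledge, so there is no figure of its own to reproduce. The check compares the variances of the two estimators.

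**Inputs**
- N = 35 evaluable, split 17/18 (Sample size; Randomization). The 35 is taken as stated, although 9% of 348 is 31.3.
- h = 1/17 + 1/18 = 0.1144.
- Assumed, because the documents do not give them: pre/post correlation ρ of 0.3, 0.5 or 0.7; equal pre and post SDs (s = 1), relaxed below.

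**Formulas, equal SDs**
- Change score: Var = 2s²(1−ρ)h, with N−2 = 33 df.
- ANCOVA: Var = s²(1−ρ²)h × (N−3)/(N−4), with N−3 = 32 df. The last factor is the small-sample cost of estimating the slope: 32/31 = 1.032.
- Ratio (ANCOVA to change score) = 1.032 × (1+ρ)/2.

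| ρ | Variance ratio | Inverse | 95% CI half-width, change score (SD) | 95% CI half-width, ANCOVA (SD) |
|---|---|---|---|---|
| 0.3 | 0.671 | 1.49 | 0.814 | 0.668 |
| 0.5 | 0.774 | 1.29 | 0.688 | 0.606 |
| 0.7 | 0.877 | 1.14 | 0.533 | 0.500 |

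For ρ = 0.5, the change-score variance is 2 × 0.5 × 0.1144 = 0.1144, the SE is 0.338, and t(33) gives 0.688. The ANCOVA variance is 0.75 × 0.1144 × 1.032 = 0.0886, the SE is 0.298, and t(32) gives 0.606.

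**Break-even.** The ratio reaches 1 when (1+ρ)/2 = 1/1.032, that is ρ = 2/1.032 − 1, about 0.94.

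**Unequal SDs.** With k = SD post / SD pre, the ratio is k²(1−ρ²) × 1.032 / (1 + k² − 2ρk).
- k = 0.8: 0.518, 0.590, 0.648 for ρ = 0.3, 0.5, 0.7.
- k = 1.2: 0.786, 0.899, 0.997.
- The maximum is 1.032, at k = 1/ρ, where the true slope is exactly 1 and only the degree of freedom is lost.

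**Chance imbalance.** The between-arm baseline difference has SD √h = 0.338 score SD at N = 35 (median absolute value 0.674 × 0.338 = 0.228) and √(2/23) = 0.295 at N = 46. Given a baseline difference D and equal SDs, the change-score estimate shifts by (1−ρ)D in favour of the arm that started lower. For D = 0.3 SD that is 0.21, 0.15 or 0.09 SD at ρ = 0.3, 0.5 or 0.7.

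**Simulation.** With N = 35 and 40,000 trials per correlation, the variance ratios were 0.67, 0.78 and 0.88, with type I error of 4.8% to 5.1% for both methods. At all 46 recruits the formula gives 0.67, 0.77 and 0.87, so the result does not depend on the exact number evaluable.

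**The case against.** The planned test is pre-specified, consistent across the document and valid; no error rate is inflated. On that view this is general advice that fits almost any trial with a score before and after. The stated aim of estimating an effect size for a later trial stands beside the treatment-success goal, and nothing says the knowledge result will size or trigger that trial. The gain cannot be derived from the documents: across the SD ratios examined it runs from about half the variance to nothing. Imbalance of 0.3 SD or more would arise in only about 37% of trials at N = 35, and the 0.15 SD shift at ρ = 0.5 is small beside a half-width of 0.69 SD. The planned baseline comparison would also reveal it.

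Much of this stands, and it limits the weight of the point. The size is conditional, and the planned interval is usually wider rather than always. Seeing an imbalance in a baseline table does not correct for it, however, and none of these points shows a material cost to ANCOVA. A bounded 16-item score does not rescue the change score either: simulation under an assumed item model gave variance ratios of about 0.33 to 0.92, with type I error near 5% for both methods.

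Two further points affect both methods equally. The exit survey goes to the intervention group and lists no knowledge items, and the TB knowledge row of Table 5 shows a single measurement mark (possibly a fault of text extraction), so how the control arm's post score is obtained is unclear. The figure of 35 also comes from the treatment-success calculation, and a questionnaire may yield fewer.

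**Conclusion.** The point holds as a minor matter of efficiency. The change-score t-test is not wrong, but ANCOVA makes better use of the same data in most plausible settings and loses at most about 3% in the worst one. The central figures, 12% to 33% less variance at N = 35, rest on equal pre and post SDs and a correlation of 0.3 to 0.7, neither of which the documents supply. If the post SD is 0.8 to 1.2 times the pre SD, the variance ratio runs from 0.52 to 1.00. Confidence is high in the direction of the gain, not in its size. The outcome is secondary and no stated decision depends on it.

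**What to change.** In the TB knowledge row of Table 5, replace the t-test with ANCOVA: post-intervention score on arm plus baseline score. Report the adjusted mean difference with its 95% CI, and keep the raw change by arm as a descriptive column. In both copies of the Data Analysis/Interpretation paragraph, add this as an exception for TB knowledge and leave the t-test rule for other continuous outcomes in place. At the same time, state when and how the post-intervention score is collected in the control arm, since either analysis needs it.

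The cost is a few words in three places and one degree of freedom. No data are needed beyond the baseline and post-intervention scores in both arms that the planned t-test already requires.

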Data collection methods: **Baseline survey** will use NINR common data elements of main and form administration and demographics using the Computer Assisted Interview.⁶² The **web based interface** will collect all incoming and outgoing messages and capture instances of participants not notifying. **Medical records or national registry** will be reviewed to collect treatment outcomes, including sputum sample results if collected or rationale why they samples were not ordered (e.g., patient without cough/sputum). Data convergence will be used to assess treatment adherence: notification of self-administration, sputum sample, report of no symptoms, and drug metabolite test results. Metabolite tests will be done in home and time-stamped through app. An **exit survey** will be given to all intervention group participants via app survey or text message and will include: Likert scale questions on acceptance (e.g., was intervention helpful in you completing your treatment, would you recommend to others), open ended questions for problems and recommendations, and 10 item Global Health PROMIS SFv1.1. I will conduct **in-depth semi-structured qualitative interviews** with a minimum of 10 intervention group participants and 5 healthcare team personnel (director, clinician, social worker, nurse, and ancillary staff). I will attempt to interview participants from each of the following groups: had abandoned treatment, had difficulties, and those who completed successfully. Interviews questions include identifying challenges, bottlenecks, if intervention meet needs, confidentiality concerns, and recommendations. Interviews will be recorded and transcribed verbatim.⁶³

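### Appointment attendance is given as a mean proportion but tested with chi-square; the two do not match, and the unit of analysis is left open

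*Combined protocol and SAP*

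**What the plan says.** Two places in the combined protocol and SAP bear directly on this.

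- **Table 5 (overview of variables, hypotheses, operationalization and data collection), appointment attendance row.** The hypothesis is intervention greater than control, the measure is "Mean proportion", the test is chi-square, and there are three measurement-point marks.
- **Data Analysis/Interpretation**, repeated under Statistical Design and Power: "Independent-sample *t*-tests will be conducted for continuous outcomes and chi-square test for dichotomous or categorical variables". The same section adds: "A p-value less than 0.05 will be set to detect a statistically significant difference for all analyses".

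Other text frames the row without defining it:

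- The Table 5 note gives the time points as "T0 Screening, T1 Baseline, T2, 2 months, T3 6 months". It reserves an asterisk for "data collected from intervention group only". The attendance row has no asterisk, so attendance is needed in both arms.
- The outcome text after Table 5 lists attendance among the secondary outcomes and says no more about it.
- Usual care describes "follow-up appointments determined by the clinician", in general monthly, so the number due can differ between patients.
- Data collection methods says that medical records or the registry "will be reviewed to collect treatment outcomes, including sputum sample results if collected". It does not name attendance under any source.

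**The concern.** The measure and the test describe different kinds of variable. A mean proportion suggests one fraction per participant, averaged within arm. A chi-square test needs counts in categories. To run it on attendance, someone must first turn the fractions into counts, and the plan does not say how. There are three obvious ways:

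- **(a)** Pool all visits in each arm and compare attended with missed. This treats repeated visits by one patient as independent.
- **(b)** Reduce each patient to yes or no, which needs a cut-off.
- **(c)** Test attendance at measurement points, which needs a named point or a rule for more than one.

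These are different outcomes with different error properties. Because the row states a between-arm hypothesis and the plan applies the 0.05 threshold to every analysis, two analysts could follow the plan in good faith and report opposite verdicts from the same data.

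**Working it through.** **Textual check.** The plan gives no attendance rate, power or error figure, so there is no figure to reproduce. Setting the row beside the test rule leaves two readings:

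| Reading of the measure | Type of variable | Test under the plan's rule | What is wrong in the row |
|---|---|---|---|
| Mean of per-participant proportions | Quantitative | t-test | The test |
| Share of patients attending | Dichotomous | Chi-square | The word mean; no cut-off or time point given |

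The neighbouring TB knowledge row pairs a change score with a t-test, as the rule requires. The attendance row has all its cells in the text available to us, so a displaced cell is unlikely. Which columns hold its three marks cannot be seen. Only T2 and T3 follow baseline, so any three of the four points must include screening or baseline, when follow-up attendance cannot yet exist.

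**Inputs for sizing the consequence**

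- From the plan: a recruitment target of 46 at 1:1 gives 46 / 2 = 23 per arm. After 20% attrition, 46 × 0.8 = 36.8, or about 18 per arm. Monthly appointments over about 6 months suggest about 6 visits. Alpha is 0.05.
- Assumed: attendance of 80% or 90%, 3 or 6 visits per patient, and an intracluster correlation (ICC) of visits within patient from 0 to 0.5. The documents give none of the attendance rates or ICCs.
- Method: beta-binomial simulation, 40,000 runs, two-sided 0.05, Pearson chi-square without continuity correction.

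**(a) Pooled visits.** The variance is understated by the design effect 1 + (m − 1) × ICC, so the true type I error is about 2 × [1 − Φ(1.96 / √(1 + (m − 1) × ICC))]. With m = 6:

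| ICC | Design effect | 1.96 / √(design effect) | Formula | Simulated (23 per arm, 80%) |
|---|---|---|---|---|
| 0 | 1.00 | 1.960 | 0.050 | 0.051 |
| 0.05 | 1.25 | 1.753 | 0.080 | 0.079 |
| 0.1 | 1.50 | 1.600 | 0.110 | 0.106 |
| 0.3 | 2.50 | 1.240 | 0.215 | 0.218 |
| 0.5 | 3.50 | 1.048 | 0.295 | 0.303 |

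For ICC 0.05 to 0.5, 3 visits give 0.061 to 0.171. With 18 per arm and 6 visits the range is 0.080 to 0.307 at 80% attendance and 0.082 to 0.311 at 90%.

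**(b) One yes/no value per patient** (all 6 attended, or at least 5 of 6). Type I error is 0.048 to 0.055 at 23 per arm and 0.038 to 0.066 at 18 per arm. The two cut-offs give opposite significance verdicts on the same data (23 per arm, ICC 0.05 to 0.5) in 6% to 8% of trials with 80% attendance in both arms, and in 22% to 34% of trials with 70% against 85%.

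**(c) Chi-square at both T2 and T3, unadjusted, either counting as success.** Type I error is 0.081 to 0.103 at 23 per arm and 0.061 to 0.094 at 18 per arm.

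**The plan's t-test on participant proportions** (6 visits, ICC 0 to 0.5). Type I error is 0.046 to 0.052 at 23 per arm and 0.043 to 0.052 at 18 per arm. Letting the number of visits vary from 2 to 7 per patient gives 0.046 to 0.052 at 23 per arm.

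**Power (23 per arm, 6 visits)**

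| Scenario | t-test | All 6 | At least 5 of 6 |
|---|---|---|---|
| 70% vs 85%, ICC 0.1 | 0.676 | 0.510 | 0.549 |
| 75% vs 90%, ICC 0.3 | 0.554 | 0.578 | 0.455 |

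Neither approach always has more power.

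**The case against.** The strongest reply is that this is a wording slip in a minor row. Attendance is secondary, the power calculation covers treatment success only, and no decision rule uses the attendance p-value. If the authors meant the share of patients attending, chi-square follows their rule and one word is wrong. The large error rates arise only if visits are pooled, which the plan never says, and they rest on an assumed ICC and attendance rate. The cut-offs compared above are also the reviewer's choice. The original table layout may show which time points are marked, and clinic records are a natural source for both arms.

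Much of this stands, and it limits the weight of the point. The inflation figures show what one permitted reading could do; they are not an error rate of the plan. The missing source and denominator are gaps in detail that would not carry the point alone. The mismatch remains, because even the benign reading leaves the row wrong and without a cut-off or a time point in words. The further objection that a t-test may fail when patients have different numbers of appointments is answered by the check with 2 to 7 visits, where the error rate held.

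**Conclusion.** The concern holds. The row is inconsistent as written, and no other part of the document reconciles it. Its size depends on the reading adopted: no material inflation for one yes/no value per patient, about 6% to 10% for either of two unadjusted time-point tests, and about 6% to 31% for pooled visits with ICC 0.05 to 0.5 and 3 to 6 visits. The firmer cost is that the outcome is undefined: two reasonable cut-offs disagree in roughly a quarter to a third of trials if attendance truly differs as 70% against 85%. All these figures rest on the stated assumptions about visits, attendance and ICC. The matter should be corrected, but it touches one secondary outcome of a pilot and not the primary analysis.

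**What to change.** In the Table 5 attendance row, define the measure as each participant's appointments attended divided by appointments due, from enrolment to 6 months, taken from the same source in both arms. Replace chi-square with the plan's independent-samples t-test on that proportion, and report the mean difference with a 95% confidence interval, which also serves the pilot's aim of estimating an effect size. Add one sentence on how appointments after default, death or transfer count in the denominator, and name the source under Data collection methods. Fix the definition before outcome data are seen.

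If a yes/no outcome was intended, chi-square can stay, but the row must drop the word mean and state the cut-off or the single measurement point.

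The cost is one table row, one sentence and one named source. Due and attended counts must be recorded per participant in both arms, which is extra data collection if clinic records do not already hold them. The sample size does not change.

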Procedures: A local health care professional (i.e. nurse) with expertise of TB treatment protocols and the healthcare system will be sought to manage and monitor the messaging system/intervention, and follow-up with participants. The health care professional will be trained on app and platform use, research goals and protocols

by the PI and the regional TB director, [name]. Participants will be informed that interaction with the healthcare staff through the app is provided within a clinic-based system and available during office hours (Monday-Friday) and that emergencies must be directed through standard routes. Participants randomized to intervention will receive verbal and written instructions as well as one-on-one demonstration of app features.

Duration and follow-up period: This study is estimated to take about 1 year and will be conducted during years 2 to 3 of this award. Participants will be followed for their full treatment course (approximately 6 months) after entering into the study. Therefore, data collection will be completed about 6 months after the last participant is enrolled into the study.

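### PROMIS Global Health is to be compared between arms, but the only collection procedure stated covers the intervention arm alone

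*Combined protocol and SAP*

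**What the plan says.** The protocol has two tables numbered 5; the one meant here is the overview of outcomes in Aim 3. Its PROMIS row, described as "CDE outcome for self-management", has the hypothesis I>C, and the table note defines I as intervention and C as control. The note also reserves an asterisk for "data collected from intervention group only". Acceptability and level of engagement carry it; PROMIS does not.

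Data Analysis/Interpretation assigns independent-sample t-tests to continuous outcomes in general. It does not name PROMIS.

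Data collection methods mentions PROMIS once, as part of the exit survey. That survey "will be given to all intervention group participants via app survey or text message and will include: Likert scale questions on acceptance", then "open ended questions for problems and recommendations, and 10 item Global Health PROMIS SFv1.1".

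The text on secondary outcomes adds that the form "includes 10 items, is available in the Spanish language, and can be integrated into REDCap", without saying who completes it or when.

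**The concern.** The table plans a comparison that needs scores from both arms, while the one stated procedure reaches one arm. This goes beyond a missing detail. MARS, WHOQoL-BREF and TB knowledge have no route in Data collection methods, whereas PROMIS has one and it is limited to the intervention group. It also runs through the app survey or text messages, and Aim 1 makes texting part of the intervention platform.

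Staff who follow the exit-survey text would not approach controls. Treatment outcomes can be taken afterwards from medical records or the registry, but a patient's own health rating at about 6 months cannot. Aim 3 is meant to rehearse the definitive trial and estimate effect size. A one-arm PROMIS measurement would give no between-arm estimate and would leave control-arm collection untested.

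**Working it through.** The plan gives no PROMIS effect size, standard deviation or power, so there is no figure to reproduce. The check compares the relevant parts of the plan and then counts the participants affected.

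**What each part supplies for PROMIS**

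| Place | What it states | End-of-treatment PROMIS from controls? |
|---|---|---|
| Outcomes table, PROMIS row and note | I>C, no asterisk | Implied, no procedure |
| Secondary outcomes text | 10 items, Spanish version, REDCap possible | Not stated |
| Baseline survey | "will use NINR common data elements of main and form administration and demographics using the Computer Assisted Interview" | No; at most a baseline score, and PROMIS is not named |
| Web interface | Messages and missed notifications | No |
| Medical records or registry | Treatment outcomes, sputum results | No |
| Exit survey | PROMIS named | No; intervention group only |
| Interviews | Intervention participants and health care staff | No |
| Duration and follow-up period | "Participants will be followed for their full treatment course (approximately 6 months) after entering into the study" | Follow-up of all, no instrument named |

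The extracted table has lost its column positions, and the PROMIS and WHOQoL-BREF rows may be merged. Nothing here depends on the number or position of the X marks or on the blank analysis cell. The end-of-treatment timing is taken from the exit survey.

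**Controls affected**

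- Inputs: 46 recruited (Sample size); 1:1 allocation in blocks of 10 (Randomization). A single unstratified list is assumed, since no stratification is stated.
- Average: 46 / 2 = 23 controls.
- Range: four full blocks give 40 participants, 20 per arm. The other 6 come from a fifth block of 5 and 5, which can supply 1 to 5 controls. The total is therefore 20 + 1 = 21 to 20 + 5 = 25.
- Controls with an end-of-treatment PROMIS score if the exit-survey text is followed: 0.

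**Burden of collecting it**

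- 23 × 10 items = 230 responses (21 × 10 = 210 to 25 × 10 = 250).
- With the plan's 20% attrition, if equal by arm: 23 × 0.8 = 18.4 controls, or 18.4 × 10 = 184 responses. The 230 is therefore an upper figure.
- TB knowledge has 5 + 4 + 2 + 5 = 16 items. Adding PROMIS to the same contact gives 16 + 10 = 26.

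**The case against.** The strongest reply is that control-arm collection was plainly intended. The Outcomes section says the table covers data collection. PROMIS has no asterisk there, the form can go into REDCap, and all participants are followed to the end of treatment. Data collection methods is not a complete list of instruments, and it nowhere says that controls will not complete PROMIS. TB knowledge also lacks a stated route, yet its wording, "TB knowledge will be assessed using items from the Tuberculosis Knowledge Assessment Questionnaire at pre and post-intervention", is readily taken to imply a post-intervention contact with controls; the same generosity could be extended to PROMIS. On this view the plan needs one clarifying sentence, for one exploratory secondary outcome in a pilot.

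Much of this stands. The intention is probably as described, the loss is conditional on the exit-survey text being followed, and the scope is narrow. The specific test is inferred from a general sentence on continuous outcomes. The parallel with TB knowledge is incomplete, however: that outcome has an explicit pre and post statement without an arm restriction, while PROMIS is explicitly placed in a one-arm survey. An inferred intention does not tell field staff to contact controls, and the only explicit instruction points the other way. A PROMIS score within the baseline common data elements, if one is collected, would not replace the missing follow-up score.

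**Conclusion.** The concern holds. The outcomes table and the exit-survey text conflict, and the procedure as written does not support the planned between-arm PROMIS comparison. If that procedure is followed, 0 of about 23 controls (21 to 25, given exactly 46 recruited and a single list) have an end-of-treatment score, so there is no between-arm estimate for this outcome.

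The mismatch in the text is certain; the loss of the comparison is conditional. The primary outcome is unaffected, and so is the sample-size statement, which concerns treatment success only. This should be fixed before enrolment because the missing scores could not be reconstructed.

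**What to change.** Reconcile the two places in one of two ways.

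1. **Keep the comparison.** Amend Data collection methods so that PROMIS is collected from both arms at the same end-of-treatment time point, preferably by the same mode and by a route that does not need the intervention app. The REDCap form already mentioned is one possibility. Only the acceptance and open-ended app questions stay intervention-only. The route is the investigator's choice; if text messages are used for controls, the plan should say how they are kept apart from the intervention platform. The cost is one amended sentence and at most about 230 item responses. The contact implied by the TB knowledge assessment could carry the form, growing from 16 to 26 items.
2. **Drop the comparison.** Add the asterisk to PROMIS in the outcomes table and remove I>C. This needs no further data collection but gives up one secondary comparison.
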